3.4.3 Anticipated number of subjects

All subjects who experience a moderate or severe infiltration will be invited back for a repeat scan. Based on historical data, Wake Forest Baptist quality improvement initiatives have been implemented to reduce the number of infiltrations. We would therefore estimate up to 20 subjects in the next twelve months. Data will also be captured on the CRF for any patients who return for additional follow-up scans (after completing the test/re-test portion of the study).

3.5 Study procedure

The LaraTM System is currently commercially available and is being used on site as part of a Quality Improvement project on all patients undergoing PET/CT studies. The LaraTM System will continue to be used on all patients undergoing PET/CT scans at the completion of the Quality Improvement Study to provide ongoing quality control and quality assurance of the injection process. Patients whose scans are determined by the Nuclear Medicine physician, or their designee, to have a moderate or greater infiltration based on review of the standard PET images and/or LaraTM TACs will be asked to return for a repeat PET/CT scan within 1-7 calendar days. In the event that the follow up scan shows any infiltration; the Nuclear Medicine physician or designee will be consulted to determine appropriate next steps. Site will duplicate the PET/CT protocol of the initial scan as carefully as possible for the follow up scan. Factors that will help ensure consistency of scan conditions to be recorded on the Case Report Form (CRF) (Appendix 1) include (but are not limited to):

- Same pre-procedure process and instructions to subject
- Time of day
- Glucose
- Time from injection to scanning
- PET/CT bed protocol
- Fasting and pre-scan activity level
- Subject weight
- BMI
- Prescribed FDG dose
- Flush volume
- Concomitant medications
- Any other data deemed pertinent by the technologist and/or Nuclear Medicine physician

3.5.1 Withdrawal of subjects due to non-compliance

Non-compliance will only occur if a subject does not follow the same pre-PET/CT scan guidance that they followed for their initial scan. In the event of reported non-compliance by a subject, the Nuclear Medicine physician will be consulted on appropriate action to take.

3.5.2 Procedures to assess efficacy

The study does not involve evaluation of efficacy.

3.5.3 Procedures to assess safety

The study does not involve evaluation of safety.

3.5.4 Schedule of study visits

Patients who are determined to have a moderate or greater infiltration on their routinely ordered PET scan will be invited back for a repeat scan within 7 days of the initial scan.

3.6 Study Objectives

3.6.1 Primary Objective

To measure the impact of moderate (or greater) infiltrations on standardized uptake values.

3.6.2 Exploratory Objectives

- To estimate the impact that infiltrations may have on initial assessment and/or response criteria assessment in accordance with PERCIST criteria.
- To measure the impact of moderate or greater infiltrations on metabolic tumor volume and total lesion glycolysis.

3.6.3 Sample size determination

The sample size of the group who will return for re-testing is challenging to forecast a priori due to ongoing quality improvement efforts to reduce infiltrations. The study will enroll patients for up to 12 months, or will be terminated at 20 patients if reached in less than 12 months.

3.6.4 Data Analysis

Upon the determination of an infiltrated subject, the technical staff will notify the Nuclear Medicine physician to determine the severity and appropriateness of the subject for the study. To qualify for the study, the subject will need:

- at least one target lesion; and

- at least a moderate infiltration as determined by visual analysis and/or infiltration score from the Lucerno Dynamics' Lara™ system software

Data will be analyzed on each individual subject after the second imaging session. The scans will be presented in tandem such that simultaneous measurements may be performed using a qualified image analysis program, such as MIM version 6.5. Up to five target lesions will be assessed, chosen to include the target lesion or lesions defined under the PERCIST criteria [8]. For each lesion, SUV peak will be measured, and a volume contour will be created using mean liver SUV+2SD as a threshold., SUVmean, metabolic tumor volume, and total lesion glycolysis will be measured from the contour. The lesions chosen will be the same for each scan, however differences in the scans may affect the volume contour. Liver and blood pool measurements will also be made as for PERCIST criteria.

SUV will be descriptively compared for the original and re-test. Our expectation is that SUV will increase at the re-test, although we are not amply powered to conduct a rigorous statistical test. We will also evaluate the relationship between SUV values and the Lara score by computing a Pearson's correlation coefficient. We hypothesize this correlation will be positive.

We hypothesize that presence of venous stasis (a cessation or impairment of venous flow) may have an influence on the relationship on SUV scores. We will conduct a sensitivity analysis by conducting analyses with and without stasis cases. Specifically, we will compare the % change in SUV values between test and re-test and the correlation coefficient of % SUV change and Lara score in the samples including and excluding stasis cases.

To assess the exploratory objective of whether extravasation of radiotracer could influence initial staging, for patients where the type of primary solid tumor is known the T, N, and M stages will be assessed to the extent possible by PET/CT for each scan and an overall stage assigned. This will be done even if the scan was performed for response assessment or follow up. No additional imaging or clinical information will be used and it is recognized that this assessment may not generate the true clinical stage. However, the comparison between the two scans will still provide information regarding the risk of changing stage based on missed or mischaracterized lesions after an extravasation event. To provide more granular information, the number of FDG avid regional nodes and number of FDG avid non-nodal metastases (capped at 25 each) will also be recorded for each scan.

For the exploratory objective of whether extravasation can influence apparent response to therapy, we will use the infiltrated and repeat scans to explore the impact of infiltrations on PERCIST criteria if there is an existing PET/CT scan for

comparison. This other PET/CT scan could either be a prior or a follow-on PET/CT scan that has a Lara-validated injection.

All scans will be analyzed by a qualified Nuclear Medicine physician and reported using the study imaging charter. Any measurements made for the clinical reports will not be used for this analysis. To mitigate bias, a second blinded radiologist will independently analyze the scans.

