DURATION OF SUBJECT PARTICIPATION AND DURATION OF STUDY	Patients who experience a moderate or greater infiltration will be invited for a repeat PET/CT scan. Subject participation in this study is limited only to the few minutes they are questioned after their first scan and before their repeat scan, and for the time it will take for the repeat scan. These questions are designed to try and ensure both scans were conducted under similar subject conditions (fasting levels, prior activity levels, etc.) The questions should not require more than 15 minutes total. Final data analysis will be completed within 3 months of enrolment of the final subject.
STATISTICS Primary Analysis Plan	Analyses will be descriptive in nature because the sample size of the group who will return for re-testing is challenging to forecast a priori. We anticipate enrolling up to 20 patients in 12 months based on the infiltration rate at WFB and accounting for ongoing quality improvement efforts.
Rationale for Number of Subjects	All subjects undergoing PET/CT who experience a moderate or greater infiltration will be invited back for a repeat scan.

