3.4.2 Exclusion criteria

- Subjects unwilling or unable to tolerate a repeat PET/CT scan.
- Subjects with meaningful medical intervention between PET/CT scans that would likely impact SUV.
- Subjects with follow-up moderate or greater infiltrations as determined by the PI and Lara score.
- Patients for whom an infiltration score cannot be determined, such as when ports or other central lines are used.

- Pregnant women.
- Subjects who are not able to read/understand English

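### Does leaving the unit of analysis (lesion or patient) unstated in section 3.6.4 undermine the SUV summaries and the Lara correlations?

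*Combined protocol and SAP*

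**What the plan says.** To enter the study a subject needs "at least one target lesion; and" at least a moderate infiltration (section 3.6.4). The same section sets the upper limit on lesions: "Up to five target lesions will be assessed, chosen to include the target lesion or lesions defined under the PERCIST criteria". SUVpeak and SUVmean are obtained for each lesion on both scans.

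Three uses of SUV follow in section 3.6.4:

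- a descriptive comparison of the original scan with the re-test;
- a step to "evaluate the relationship between SUV values and the Lara score by computing a" Pearson coefficient;
- a sensitivity analysis with and without venous stasis, in which "we will compare the % change in SUV values between test and re-test and the correlation coefficient of % SUV change and Lara score".

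None of these names the lesion or the patient as the unit. There is no rule for reducing several lesions to one patient value, and no method for within-patient clustering.

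The study's size is expressed in patients only. Section 3.6.3 says that "The sample size of the group who will return for re-testing is challenging to forecast a priori" and that enrolment "will be terminated at 20 patients if reached in less than 12 months". The Statistics entry of the synopsis states: "Analyses will be descriptive in nature". Section 3.6.4 adds that the study lacks the power for a rigorous test.

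**The concern.** Each lesion has its own SUV, but the Lara score describes an injection. Section 3.4.2 excludes "Patients for whom an infiltration score cannot be determined", which fits one score per patient, although the documents do not say so outright. An analyst who enters every lesion as a row would repeat one score up to five times and give a five-lesion patient five times the weight of a one-lesion patient.

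Three things would then depend on an unstated choice:

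- the value of r;
- the mean % change, if lesion number is related to the size of the effect;
- the reported n.

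An n counted in lesions would suggest more information than there is, because a patient's lesions share one infiltration. The choice could also be made after both results had been seen, and section 3.6.4 states directional expectations: SUV higher at re-test, and a positive correlation with the score.

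**Working it through.** **Inputs from the documents.** At most 20 patients (section 3.6.3); one to five lesions each (section 3.6.4). The plan gives no alpha, power, effect size or standard deviation, so it has no figure of its own to reproduce.

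**Assumed input.** The documents give no intraclass correlation (ICC) for lesion SUV change within a patient. The range 0.3 to 0.9 is used below, except where 0.2 to 0.8 is stated.

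**1. Count.** By patient, n is at most 20. By lesion, n is at most 20 × 5 = 100. With design effect 1 + (5 − 1) × ICC, 100 lesions carry the information of 100/1.8 = 55.6, 100/3.0 = 33.3 and 100/4.2 = 23.8 independent observations at ICC 0.2, 0.5 and 0.8.

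**2. Size of r with five lesions in every patient.** Pooled r = patient-mean r × √(ICC + (1 − ICC)/5). For a patient-mean r of 0.50:

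| ICC | Term under the root | Pooled r |
|---|---|---|
| 0.3 | 0.44 | 0.33 |
| 0.5 | 0.60 | 0.39 |
| 0.7 | 0.76 | 0.44 |
| 0.9 | 0.92 | 0.48 |

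Five lesions in every patient is the extreme case. Section 2.0 defines SUV by normalizing to injected activity, so dose lost at the injection site would tend to scale all of a patient's lesions together. That makes a high ICC for % change plausible, and at high ICC this attenuation nearly disappears.

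**3. Difference in r with unequal lesion counts.** Simulation with 20 patients, one to five lesions each, true patient-level correlation 0.5, and 5,000 runs per setting. The table shows the absolute difference between pooled and patient-mean r within the same data set.

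| ICC | Median | 90th percentile |
|---|---|---|
| 0.3 | 0.099 | 0.207 |
| 0.5 | 0.082 | 0.178 |
| 0.7 | 0.064 | 0.148 |
| 0.9 | 0.050 | 0.136 |

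For comparison, the Fisher-z 95% interval for r = 0.50 with 20 patients is tanh(atanh 0.50 ± 1.96/√17), which is 0.07 to 0.77, a width of 0.70. The median difference is 0.05/0.70 = 7% to 0.10/0.70 = 14% of that width. In one data set in ten it is at least 0.14/0.70 = 20% to 0.21/0.70 = 30%.

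**4. Mean % change.** Suppose 4 of 20 patients have five lesions and 16 have one. Those 4 supply 20 of 36 records (56%). If they averaged +20% and the others +40%:

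- by patient: (4 × 20 + 16 × 40)/20 = 36%;
- by lesion: (20 × 20 + 16 × 40)/36 = 28.9%.

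The 20% and 40% are illustrative. Nothing in the documents links lesion number to the effect of an infiltration, and without such a link the two means have the same expectation.

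**5. Error rates, only if a test were added.** With no true association and 20 patients, a nominal 5% Pearson test on pooled lesions rejects in:

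- 11.4% to 24.3% of runs for the 4 × 5 + 16 × 1 mix;
- 14.4% to 29.3% with one to five lesions each;
- 18.6% to 38.1% with five lesions each.

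On patient means the rate is 4.4% to 5.5%. The plan commits to no such test, so these figures describe an analysis outside it.

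**The case for a change.** The strongest argument for a change is that the descriptive numbers are themselves the study's result. Calling the analysis descriptive does not make r, the mean % change or n reproducible from the text. The sentence on analysing each subject's data concerns timing, after the second session. The reference to PERCIST does not settle the unit either, because the assessed lesions need only include the PERCIST targets. Even a patient-level reading leaves the per-patient summary open. One sentence would close the gap at no cost in data, and would prevent a choice made after the results are known.

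Most of this stands as a description of the text. Section 3.6.4 is silent, and writing the unit down would be good practice. Whether the imaging charter it mentions, or the case report form, addresses the unit cannot be seen here, and nothing in this conclusion relies on them.

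The argument does not show that the plan is wrong. Silence is not an instruction to pool. Everything the plan counts, it counts in patients, so one value per patient fits the text at least as well. A per-lesion description is also legitimate in a study whose title concerns the uptake values of target lesions, provided it is labelled as such. The room for a post hoc choice is limited by its visibility: enrolment stops at 20 patients, so a reported n above 20 could only be a lesion count.

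**Conclusion.** The concern does not call for a change. Section 3.6.4 leaves a definition unwritten, and a competent analyst can fill it sensibly: one value per patient wherever SUV is set against a patient's single Lara score, both patient and lesion counts reported, and any per-lesion description labelled.

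No stated error rate, power or rule is wrong, because none is stated for these analyses. On what is planned, the choice moves r by a median of 0.05 to 0.10, and by at least 0.14 to 0.21 in one data set in ten. This is small beside the uncertainty that 20 patients leave in any case. The mean % change shifts in expectation only if lesion number is related to the effect, which the documents do not suggest.

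These sizes rest on an assumed ICC of 0.3 to 0.9, a true patient-level correlation of 0.5, the full 20 patients, and one Lara score per patient. The conclusion also depends on the analyses staying descriptive. A p-value or interval computed on pooled lesions as if they were independent would be misleading, but the plan proposes neither.

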1.0 INTRODUCTION AND BACKGROUND

PET/CT scanning is becoming progressively more important to the management of patients with cancer due to its accuracy and convenience in presenting anatomical and functional information. Oncology PET/CT scans are often used to stage cancer and assess therapy response. Quantification of PET/CT results is increasingly being used. A widely used semi-quantitative parameter to assess tumor status is the standardized uptake value (SUV). SUV estimation accuracy can be impacted by many variables. Therefore, producing high quality PET/CT images requires rigorous protocols of image acquisition and analysis.

Today, there still exists a significant amount of variability in PET/CT results in test and re-test studies [1]. This variability can be introduced by instrumentation and patient-specific factors. Variability reduces image quality and increases the required changes in tumor quantification to reflect real tumor response or progression. Weber's recent multi-center study of NSCLC found a 30% SUV decrease (in defining therapeutic response) or a 40% SUV increase (in defining progression) is required to have confidence that the results are indicative of metabolic response or metabolic progression, rather than a reflection of variability in the measurement of the PET/CT process [2].

Accurate SUV calculation requires that the entire net injected dose of radiolabeled tracer is administered intravenously as a bolus. The quality and quantification of a PET/CT image is highly dependent on the uptake of radiolabeled tracer. Boellaard et al. have indicated infiltrations could potentially underestimate SUV measurements by as much as 50% [3]. Infiltrations and obstructions are not uncommon. Single center studies have demonstrated that improper injections of radiolabeled tracer for PET can occur in 10 - 21% of cases [4, 5, 6].

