3.4 Subject selection

3.4.1 Inclusion criteria

Subjects with solid tumors or lymphoma undergoing F-18 FDG PET/CT scan who have at least one measurable target lesion and sustain a moderate or greater infiltration.

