8.0 ADDITIONAL RECORDS AND REPORTS

8.1 Data handling and record-keeping

Data will be captured using the Lara™ System, the site PET/CT scanner and a study CRF. Other than the scintillation data captured, the following information is also captured via drop down menus on the home screen at the time of data download:

Subject Height - in or cm

Subject Mass – lb. or kg

Subject Age Group: <16, 16-49, 50-69, >70

Subject Glucose:

Radiotracer:

Dose (mCi):

NM Technologist performing the injection

Flush Volume:

Injection Orientation – Unknown, Right, Left

Injection Locations – Unknown, Antecubital, Forearm, Hand, Wrist, Foot, Port, Other

Injection Technique – Unknown, Butterfly, IV, IV Drip, Straight Stick, Other

Auto Injection – Unknown, No, Yes

Needle Gauge – Unknown, 14, 16, 18, 20, 22, 23, 24, 25

At the time of data entry, the NM Technologist enters the subject's identifying hospital record number. This number is cross-referenced to a Lucerno identification number to allow the site to identify the subject and match the data with the subject. The cross reference between the hospital and Sponsor numbers is recorded at the site. Only Lucerno's identification number is transmitted, with other collected data, to the Lucerno server. The transmission is encrypted and contains no Protected Health Information.

Completed case report forms will be scanned and sent via secure e-mail to Lucerno Dynamics on a pre-determined schedule. All study documents, including paper case report forms will be kept in a secured, locked location at Wake Forest Baptist Medical Center.

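### Target nodes that drain the infiltrated site are neither flagged nor examined separately, so they could dilute or blur the SUV change and its correlation with the Lara score.

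*Combined protocol and SAP*

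**What the plan says.** Section 3.4.1 admits "Subjects with solid tumors or lymphoma undergoing F-18 FDG PET/CT scan who have at least one measurable target lesion", provided the infiltration is at least moderate. Section 3.6.4 repeats the minimum as "at least one target lesion; and" and gives the selection rule: "Up to five target lesions will be assessed, chosen to include the target lesion or lesions defined under the PERCIST criteria". Neither these rules nor the exclusions in 3.4.2 refer to where a lesion lies relative to the injection. The lesion set is fixed across scans: "The lesions chosen will be the same for each scan, however differences in the scans may affect the volume contour". The plan states the direction it expects: "Our expectation is that SUV will increase at the re-test".

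The SUV comparison in 3.6.4 is descriptive. Besides it, the section plans a Pearson correlation with the Lara score, and one sensitivity analysis that repeats the % SUV change and its correlation with the score with and without venous stasis cases. There is no counterpart by lesion location.

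Section 8.1 records the side, "Injection Orientation – Unknown, Right, Left", and a location list that covers arm sites and the foot. Neither item is used in the analysis. Section 3.6.4 does foresee "missed or mischaracterized lesions after an extravasation event", but only for exploratory staging, where it also counts FDG-avid regional nodes.

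**The concern.** Section 1.0 cites a source under which "infiltrations could potentially underestimate SUV measurements by as much as 50" percent. That describes one mechanism: less tracer reaches the lesion through the blood, so SUV is too low on the infiltrated scan and recovers at re-test.

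A node on the drainage path from the leak can be subject to a second, opposite mechanism. It may receive leaked tracer through the lymphatics, which offsets or outweighs what it loses through the blood. Its SUV would then rise less than that of other lesions, or fall. Nothing in 3.6.4 keeps such a node out of the target set, and because the same lesions are used on both scans it would enter the paired comparison.

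Two summaries are exposed. The SUV change could look smaller and more variable than it is in lesions fed only by blood. The correlation with the Lara score could weaken, because a larger leak offers more tracer to drain; this assumes that the score rises with severity. Metabolic tumor volume, total lesion glycolysis and the regional node count on the infiltrated scan could be affected in the same way.

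**Working it through.** The plan has no effect-size or power figure to reproduce; 20 is an enrolment cap (3.6.3). What follows is illustration.

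**Inputs**
- From the documents: at most 20 patients (3.6.3); one to five lesions per patient (3.6.4).
- Assumed: a 20% SUV loss in every other lesion on the infiltrated scan, so a re-test/original ratio of 1/0.80 = 1.25; k = 2 affected patients; one draining node in each, reading f = 1.25, 1.5 or 2.0 times its true value on the infiltrated scan, so its ratio is 1/f. Patients are averaged on the log scale. The plan does not specify that summary; it is used here only to show size.

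**Formula**
With m lesions per affected patient, one of them the node, that patient's mean log ratio is d = [(m − 1) × ln 1.25 − ln f]/m. The mean over patients is [(20 − k) × ln 1.25 + k × d]/20, and the apparent loss is 1 − exp(−mean). Here ln 1.25 = 0.2231.

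**Results for k = 2**

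| Node's place | f = 1.25 | f = 1.5 | f = 2.0 |
|---|---|---|---|
| Only lesion (m = 1) | 16.3% | 14.8% | 12.3% |
| One of five (m = 5) | 19.3% | 19.0% | 18.5% |

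Worked cases for f = 2.0:
- m = 1: d = −0.6931; mean = (18 × 0.2231 − 2 × 0.6931)/20 = 0.1315; loss = 1 − exp(−0.1315) = 12.3%.
- m = 5: d = (4 × 0.2231 − 0.6931)/5 = 0.0399; mean = (18 × 0.2231 + 2 × 0.0399)/20 = 0.2048; loss = 18.5%.

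**Other counts, node as only lesion, f from 1.25 to 2.0**
- k = 0: 20%, unchanged.
- k = 1: 18-16%. If that node merely shows no change, the loss is 1 − exp(−19 × 0.2231/20) = 19.1%.
- k = 3: 14-8%.

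**Spread**
Section 1.0 quotes a 30% decrease and a 40% increase as the changes needed to exceed measurement variability. Reading these as 95% limits (an assumption) gives an SD of the log ratio of (ln 1.40 − ln 0.70)/(2 × 1.96) = 0.177. With k = 2 and f = 1.5, sole-lesion nodes differ from the rest by ln 1.25 + ln 1.5 = 0.629, so the SD becomes √(0.177² + 0.1 × 0.9 × 0.629²) = 0.259. With the node as one of five, the difference is 0.629/5 = 0.126 and the SD is √(0.177² + 0.09 × 0.126²) = 0.181.

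**Within one patient**
On the % change scale the other lesions rise 25%. A node reading 100% too high falls 50%. The patient's mean change is −50% if it is the only lesion, (25 − 50)/2 = −12.5% with two lesions, and (4 × 25 − 50)/5 = +10% with five.

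**Chance that the issue arises**
If a share p of patients has such a target, the chance of at least one among 20 is 1 − (1 − p)^20: 33% for p = 2%, 64% for 5%, 88% for 10%, 99% for 20%. The documents give no value of p.

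**The case against.** The strongest objection is that the mechanism and every size come from outside the documents, which speak only of underestimated SUVs and missed or mischaracterized lesions. That stands. The point can be put only as a possibility, and at p = 2% it is more likely than not (67%) that no patient is affected.

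A reader might infer that the plan's primary estimate is biased toward zero by a material amount. The documents do not support that. Section 3.6.4 specifies no pooled mean and no test of SUV change, and analyzes data subject by subject. The larger figures arise only when the node is a patient's sole lesion.

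A reader might also infer that such nodes should be removed from the main analysis. That does not follow either. The objective is to characterize the impact of infiltration on SUVs, and a falsely high node is one such impact. Removing lesions expected to contradict the hypothesis would also favor it, in a study sponsored by the maker of the detection device.

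The imaging charter named in 3.6.4 is not among the documents, and only the heading of the CRF appendix is visible. Either may hold a location rule; if so, 3.6.4 should refer to it. The Nuclear Medicine physician's judgment of appropriateness concerns the subject, not the lesion. A listing of at most 20 patients might show an odd node, but a reason offered after the values are seen is weaker than a flag set beforehand.

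**Conclusion.** The gap is in the text: nodal targets are eligible, one lesion suffices, no rule considers drainage from the injection site, and the recorded side and location go unused. The direction follows if a draining node takes up leaked tracer.

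The size is uncertain and often small. With a 20% loss elsewhere and 2 of 20 patients affected by a node 25-100% too high, the apparent loss is about 19% when the node is one of five lesions, 16-12% when it is the only one, and unchanged if no such node occurs. The effect on a single patient's result, or on a correlation in so few patients, can be more visible. Confidence is low on frequency and magnitude, but not on the absence of a rule in the supplied text. This supports a prespecified sensitivity analysis and nothing stronger.

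**What to change.** Add to 3.6.4:

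> Using the recorded injection side and location of the infiltrated scan, target nodes in the regional drainage of that injection site (arm or leg) will be flagged before SUVs are read. The % SUV change and its correlation with the Lara score will be reported with and without flagged nodes, as for stasis cases, and flagged nodes will be listed separately. Where side or location is Unknown, it will be taken from the images or source record, or the lesion will be listed as unclassifiable.

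The flag refers to the infiltrated scan only, because 3.4.2 already excludes subjects with a moderate or greater infiltration at follow-up. The leg is included because the foot is a listed injection location.

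Cost: one CRF flag, built on data already captured, and one extra sensitivity analysis. The version without flagged nodes has fewer lesions, and loses any patient whose only target is flagged.

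### The statement that the study lacks power for a test of the SUV change has no calculation behind it and, on the protocol's own repeatability figures, looks too pessimistic for moderate or large effects

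*Combined protocol and SAP*

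**What the plan says.** Section 3.6.4 (Data Analysis) sets out the primary comparison in one sentence: "SUV will be descriptively compared for the original and re-test". It then gives a direction, "Our expectation is that SUV will increase at the re-test", and declines to test it because "we are not amply powered to conduct a rigorous statistical test".

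The Statistics entry of the synopsis gives a second reason: "Analyses will be descriptive in nature because the sample size of the group who will return for re-testing is challenging to forecast a priori". Section 3.6.3 fixes only an upper limit: "The study will enroll patients for up to 12 months, or will be terminated at 20 patients if reached in less than 12 months".

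Two background figures in Section 1.0 bear on power, although the protocol does not use them for planning. A cited multi-center repeatability study in NSCLC "found a 30% SUV decrease (in defining therapeutic response) or a 40% SUV increase (in defining progression) is required" before a change can be separated from measurement variability. A second source is cited for the possibility that "infiltrations could potentially underestimate SUV measurements by as much as 50" percent.

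**The concern.** Each patient is scanned twice within about a week, under conditions matched as closely as possible, so each is their own control. Power then depends on the noise of one within-patient change, the mean effect and the number of pairs. The protocol quotes a figure for the first, a ceiling for the second and a cap for the third, but never combines them. It simply asserts the conclusion about power.

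The stake is the primary objective, which is to characterize or measure the effect of infiltration on SUV. As written, no interval or test is pre-specified for it. A clear shift could be reported only descriptively, and an absent shift could be put down to a lack of power that nobody calculated. An uncertain final sample size does not require this, because a paired analysis is valid at whatever number of pairs accrues.

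**Working it through.** The protocol states no power figure, so there is nothing to reproduce. The check asks what its quoted figures imply.

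**Inputs**
- Change thresholds of -30% and +40% (Section 1.0). Their coverage is not stated; 95% is assumed, with 90% as a sensitivity case.
- Maximum of 20 patients (Section 3.6.3). No minimum is given; 10 and 5 pairs are illustrative.
- Ceiling of 50% underestimation (Section 1.0). No mean or spread is given.
- Assumed here: paired t-test on the log ratio, two-sided 5%, one value per patient.

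**Noise of one paired change (log scale)**
- ln(1.40)/1.96 = 0.172 and -ln(0.70)/1.96 = 0.182; average 0.177.
- As 90% limits: ln(1.40)/1.645 = 0.205 and -ln(0.70)/1.645 = 0.217; average 0.211.
- With an assumed between-patient SD of the true log effect of 0.2 or 0.3: √(0.177² + 0.2²) = 0.267 and √(0.177² + 0.3²) = 0.348.

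**Effect.** If the infiltrated scan loses a fraction L of the SUV, the log ratio of re-test to initial is d = -ln(1 - L). A mean loss below is 1 - exp(-d), where d is the mean log ratio.

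**Detectable loss.** Power is P(T > t(0.975, n-1)), where T is noncentral t with n-1 degrees of freedom and noncentrality d√n/SD. For 80% power, d/SD must be 0.660 at n = 20, 0.996 at n = 10 and 1.682 at n = 5. For example, at n = 20, 0.660 × 0.177 = 0.117, and 1 - exp(-0.117) = 11.0%.

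| Total SD | n = 20 | n = 10 | n = 5 |
|---|---|---|---|
| 0.177 (repeatability only, 95% limits) | 11% | 16% | 26% |
| 0.211 (repeatability only, 90% limits) | 13% | 19% | 30% |
| 0.267 (0.177 plus spread 0.2) | 16% | 23% | 36% |
| 0.348 (0.177 plus spread 0.3) | 21% | 29% | 44% |

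**Power at given mean losses** (SD 0.177 / 0.267 / 0.348)

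| Mean loss | n = 20 | n = 10 |
|---|---|---|
| 10% | 71% / 39% / 25% | 39% / 20% / 14% |
| 20% | >99% / 94% / 78% | 94% / 65% / 44% |
| 30% | >99% / >99% / 99% | >99% / 96% / 82% |

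**Precision.** The 95% interval half-width is t(0.975, n-1) × SD/√n. For SD 0.177 and 0.348 it is 0.083 and 0.163 at n = 20, and 0.126 and 0.249 at n = 10. An observed mean change of zero would therefore leave losses of up to 1 - exp(-0.083) = 8% to 1 - exp(-0.163) = 15% open at n = 20, and 12% to 22% at n = 10.

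**The case against.** A reader might infer that the power statement is simply false and that 10 to 20 patients guarantee high power. The documents do not support that, for four reasons.

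- **No expected effect.** The 50% figure is a ceiling, and Section 3.6.4 gives only a direction. At a mean loss near 10% the statement is fair.
- **The noise is not fixed.** The thresholds come from NSCLC, with neither coverage nor SUV measure stated. This study takes any solid tumor or lymphoma and all infiltrations of moderate severity or worse, so the change is likely to vary more than repeatability alone. The spreads of 0.2 and 0.3 are assumptions.
- **No minimum sample size.** Twenty is a cap, quality improvement work is meant to reduce infiltrations, and Section 3.4.2 excludes patients whose repeat scan is also infiltrated. Evaluable pairs may be few.
- **The objective is to characterize, not to test.** Section 3.6.4 already plans percent change with and without stasis cases, and correlations with the Lara score.

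All four stand as limits on the claim. None is a reason to leave the primary comparison without inference. An unforecastable sample size rules out promising a fixed power; it does not rule out a pre-specified paired estimate with an interval, or a table of detectable effects by number of pairs. An objective to measure an effect is served by that interval even if the test is given little weight.

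**Conclusion.** The claim of inadequate power is unsupported, and the protocol's own repeatability figures suggest that it is too pessimistic for moderate or large mean losses. With 20 evaluable pairs, 80% power is reached at a mean loss of about 11% to 21%; with 10 pairs, at 16% to 29%; with 5 pairs, at 26% to 44%. The lower figure in each range is for repeatability noise alone, and the higher one adds a between-patient SD of 0.3.

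These results rest on reading the thresholds as 95% limits, on their carrying over from NSCLC to this population, and on assumed effect spreads. Reading them as 90% limits moves the repeatability-only figures to 13%, 19% and 30%. For mean losses of about 10% or less, the study is not well powered on any of these assumptions. The stronger conclusion, that the statement is wrong outright, would need an expected mean loss that the documents do not supply.

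**What to change.** In Section 3.6.4 and the synopsis, replace the blanket power clause and the forecasting reason with a pre-specified primary analysis:

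- One value of log(re-test SUV / initial SUV) per patient, from one named SUV measure and one stated way of combining lesions. Both must be chosen, because Section 3.6.4 measures SUVpeak and SUVmean on up to five lesions.
- A geometric mean ratio with its 95% confidence interval and a two-sided paired t-test at 5% (a one-sample t-test on the log ratios), with the Wilcoxon signed-rank test as a check. With five pairs the smallest two-sided Wilcoxon p-value is 2 × (1/2)^5 = 0.0625, so that check needs at least six.
- The detectable mean loss by number of evaluable pairs, with the SD assumptions shown, and a plain statement that the study is not powered for mean losses of about 10% or less.

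This takes a short paragraph and a small table, with no added patients, scans or data. The downside is that the sponsor commits in advance to one measure and one test, and the interval may be wide if few patients return.
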